The EPI-MAL-002 study started in Q4 2015 and will last for approximately 5 years (depending on recruitment timelines). EPI-MAL-003 *started in Q1 2019* when the vaccine *became* available in the study sites that are exposed clusters after its implementation according to WHO guidelines in the framework of the MVIP (first vaccine introduction *was* foreseen in 2018, see section 9.2).

(Amended 5 May 2020)

In parallel with both EPI-MAL-002 and EPI-MAL-003, a third study (EPI-MAL-005) is conducted to measure malaria transmission intensity (MTI) and other malaria control interventions at community level in the study site areas. This study began in Q4 2014, at the first malaria transmission peak season in the West African sites with peak malaria transmission in the second half of the year, and will run through the completion of EPI-MAL-003. It is taking place in similar if not identical settings as EPI-MAL-002 and EPI-MAL-003.

Finally, describing the overall morbidity and mortality in this population is thought to have broader utility beyond these malaria studies, and could serve as baseline data for other disease control and prevention studies.

CONFIDENTIAL115055 (EPI-MALARIA-002 VS AME)
Protocol Amendment 7 Final**8. RESEARCH QUESTION AND OBJECTIVES****8.1. Co-primary objectives**

- To estimate the incidence of AESI², and of other AE leading to hospitalisation or death, in children, prior to implementation of RTS,S/AS01_E.
- To estimate the incidence of aetiology-confirmed meningitis, in children, prior to implementation of RTS,S/AS01_E.

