Note: There might be an overlap of studies EPI-MAL-002 and EPI-MAL-003. Therefore, children enrolled in active surveillance of EPI-MAL-002 and who meet the eligibility criteria for the EPI-MAL-003 study may have their study conclusion for the EPI-MAL-002 study before the end of the 44 months of active follow-up if enrolled in EPI-MAL-003 (see Section 9.2.7.1.12).

[figure not shown]
Enhanced hospitalisation surveillance:

All children under the age of 5 years of age, within the study areas, not already enrolled in the active surveillance (because parents/ LARs declined enrolment in active surveillance or because recruitment had been completed) or not eligible for active surveillance, are eligible for enrolment in enhanced hospitalisation surveillance during any hospitalisations throughout the whole study period, to allow data collection regarding those hospitalisations (see [Figure 1](#) and Section 9.2.7.2). For the purpose of this study, hospitalisation is defined as spending at least one night at a health care facility.

In this protocol, active surveillance will refer to children who are enrolled in active surveillance, and enhanced hospitalisation surveillance will refer to children who are enrolled in enhanced hospitalisation surveillance. Data collected regarding the hospitalisation will be uniformly collected whether the child is enrolled in active surveillance or in enhanced hospitalisation surveillance.

Because of a possible overlap of studies EPI-MAL-002 and EPI-MAL-003, study conclusion of EPI-MAL-002 for children enrolled in enhanced hospitalisation surveillance will be done at start of study EPI-MAL-003 (as the RTS,S/AS01_E vaccine becomes available in the sites that are exposed clusters).

CONFIDENTIAL

115055 (EPI-MALARIA-002 VS AME)
Protocol Amendment 7 Final**Figure 1** Study design overview

* Hospitalisation is defined as spending at least one night at a health care facility

V = visit; W = week(s); M = month(s); SC = study conclusion (i.e. study end or child reaches 5 years of age, whichever occurs first); Enrol = enrolment.

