9.2.4. Study period

Recruitment for active surveillance is expected to be done until the enrolment target is reached. Enrolment in enhanced hospitalisation surveillance has been early terminated for the sites where the RTS,S/AS01_E vaccine will not be implemented. For the sites where the RTS,S/AS01_E vaccine will be implemented, the enrolment in enhanced hospitalisation surveillance will end at start of study EPI-MAL-003.

Active surveillance will last 44 months for each subject (mimicking 24 months of active follow-up after the 4th dose of RTS,S/AS01_E in EPI-MAL-003) except for subjects enrolled from Burkina Faso sites for whom their participation in the study has been early terminated. The EPI-MAL-002 study will last for approximately 5 years (depending on recruitment timelines).

Note: There might be an overlap of studies EPI-MAL-002 and EPI-MAL-003, some children enrolled in EPI-MAL-002 may have the possibility to be part of EPI-MAL-003 (see Section [9.2.7.1.12](#) for more details).

The study began enrolment during Q4 2015.

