In the event of death occurring at home, the cause of death will be systematically obtained through verbal autopsy using the INDEPTH Standard Verbal Autopsy Questionnaire [[INDEPTH](#), 2003] as is routinely done in the study area.

If a site is not part of the INDEPTH network, or does not have an equivalent surveillance system in place, the INDEPTH procedures for verbal autopsy might be implemented to ensure consistency across study sites.

CONFIDENTIAL115055 (EPI-MALARIA-002 VS AME)
Protocol Amendment 7 Final**9.2.7.1.12. Study conclusion**

Subjects will exit the study when they reach 5 years of age or at study end (whichever occurs first), if not earlier due to migration or in the event of death.

At the study conclusion (home visit, V10), a record will be taken of the subject's health and vital status, any disabilities and all vaccinations received.

The investigator will review collected data to ensure accuracy and completeness and will complete the Study Conclusion screen in the eCRF.

Note: There might be an overlap of studies EPI-MAL-002 and EPI-MAL-003. Children enrolled in active surveillance of EPI-MAL-002, and not eligible for RTS,S/AS01_E vaccination or declining vaccination will continue to be followed up to the study conclusion visit in EPI-MAL-002. Children enrolled in active surveillance of EPI-MAL-002, and becoming vaccinated with RTS,S/AS01_E will have their study conclusion of EPI-MAL-002. Thereafter, these children can be eligible and enrolled in EPI-MAL-003 according to the inclusion/ exclusion criteria and the EPI-MAL-003 recruitment procedures. For children enrolled in enhanced hospitalisation surveillance of EPI-MAL-002, study conclusion of EPI-MAL-002 will be done at start of study EPI-MAL-003 (as the vaccine becomes available in the study sites that are exposed clusters). Thereafter, these children can be eligible and enrolled in active surveillance or in enhanced hospitalisation surveillance of EPI-MAL-003 according to the inclusion/ exclusion criteria and the EPI-MAL-003 recruitment procedures.

CONFIDENTIAL

115055 (EPI-MALARIA-002 VS AME)
Protocol Amendment 7 Final

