9.3.1. *Co-primary endpoints*

In children living in the study area, prior to implementation of RTS,S/AS01_E:

- Occurrence of AESI (see Section 9.2.5.1 for definition).
- Occurrence of other AE leading to hospitalisation or death (see Sections 9.2.5.2 and 9.2.5.8 for definitions).
- Occurrence of aetiology-confirmed meningitis (see Section 9.2.5.3 for case definition).

9.3.2. *Secondary endpoints*

In children living in the study area, prior to implementation of RTS,S/AS01_E:

- Occurrence of probable meningitis (final classification) (see Section 9.2.5.3 for case definition).
- Occurrence of clinically suspected meningitis (final classification) (see Section 9.2.5.3 for case definition).
- Occurrence of meningitis cases identified at site level (first line laboratory) (see Section 9.2.5.3 for case definition).
- Occurrence of hospitalisation (including those attributed to an AESI, other AE, meningitis, or malaria) or death.

CONFIDENTIAL

115055 (EPI-MALARIA-002 VS AME)
Protocol Amendment 7 Final

- Occurrence of febrile convulsions during the 7-day period (Days 0-6) and 1-month period (Days 0-29) following administration of routine EPI vaccines (see Section 9.2.5.4 for case definition).
- Occurrence of two events used as surveillance quality indicators: abscess at injection site during the 7-day period (Days 0-6) following any routine vaccination and foot positional deformation (see Section 9.2.6 for case definitions).
- Occurrence of episodes of malaria using RDT and/or microscopy
 - Any malaria (including *P. falciparum* malaria) (see Section 9.2.5.5 for case definition).
 - Severe malaria (including *P. falciparum* malaria) (see Section 9.2.5.5 for case definition).
 - Cerebral malaria (see Section 9.2.5.5 for case definition).
- Occurrence of anaemia (see Section 9.2.5.6 for case definitions) at hospital entry among hospitalised children.
- Occurrence of hospitalisation
 - All causes and hospitalisations for any malaria (including *P. falciparum* malaria), severe malaria (including *P. falciparum* malaria) and cerebral malaria (see Section 9.2.5.7 for case definitions).
- Occurrence of death
 - All causes and malaria attributed deaths (including *P. falciparum* malaria attributed death) (see Section 9.2.5.8 for case definitions).
 - AE attributed deaths (see Section 9.2.5.8 for case definitions).

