9.9. Limitations of the research methods

The Protocol Amendment 4 was taking into account a follow-up of children up to the age of 5 years, with baseline events collected for each subject in the active surveillance over 44 months (mimicking 24 months of active follow-up after the 4th dose of RTS,S/AS01_E in EPI-MAL-003). The study will enrol children in the two age groups in which the Phase III study MALARIA-055 was conducted (6-12 weeks at first dose and 5-17 months at first dose) to collect background data in both age groups. However, in the post-implementation safety study EPI-MAL-003, only the 5-17 months age group will be kept.

The Protocol Amendment 5 described the sample size reduction from 40,000 to 30,000 with at least 20,000 children to be enrolled where the RTS,S/AS01_E vaccine will be implemented. There was a resultant reduction in the size of the two study groups to 15,000 subjects each (with at least 10,000 children in sites where the vaccine will be implemented).

At the start of this study, some uncertainties remained regarding the recommendations for use of RTS,S/AS01_E in SSA, and what will be the vaccine uptake at the start of the vaccine programme implementation. Therefore, one or several amendments were needed during the course of the study. Participating countries have been identified because they have active HDSS or equivalent surveillance system sites and are representing moderate/high transmission of malaria. Other sites in SSA settings with moderate-to-high transmission of malaria, from the 3 countries where the RTS,S/AS01_E vaccine will be implemented (see Section 9.2), were added to the already defined study sites. The transition from EPI-MAL-002 (pre-implementation) to EPI-MAL-003 (post-implementation) is expected to occur in the study sites from Kenya and Ghana. The possible switch from a subject enrolled to EPI-MAL-002 to EPI-MAL-003 (if eligible) will be detailed in the EPI-MAL-003 protocol. GSK acknowledges that, in addition, the study start of EPI-MAL-003 might vary according to vaccination schedule and timing of vaccine implementation in each country.

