### **4.1. Co-Primary endpoints**

In children living in the study area, prior to implementation of RTS,S/AS01E:

- Occurrence of AESI.
- Occurrence of other AEs leading to hospitalisation or death.
- Occurrence of aetiology confirmed meningitis.

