#### 6.9.3.3. Incidence in children < 5 years

The IR of each and any AESI, of each and any other AE leading to hospitalisation or death (classified by the MedDRA SOC and PT level) and of aetiology confirmed meningitis will be estimated in all children < 5 years per 100,000 person per year. A 95% CI will be computed per year and overall using an exact method for a Poisson variable.

The numerator will be the number of cases of specified events (i.e. AESI) during the study period (in both AS and EHS grouped) and the denominator will be the person-years contribution of children in all communities < 5 years of age. The denominator will be computed using the census data. A census done at least once a year will provide the total number of children under 5 years.

For example, considering 5 census done between January 2015 and January 2017, a first subject recruited in March 2015 and a last subject recruited in April 2017:

The person-year (PY) will be computed as:

$$PY = N1 \cdot \text{Period1} + N2 \cdot \text{Period2} + N3 \cdot \text{Period3} + N4 \cdot \text{Period4} + N5 \cdot \text{Period5}$$

Contrary to the computation of IR following EPI vaccine or virtual vaccination where only the first event is counted in the numerator, for IR in children < 5 years, in case a subject had more than once the same AESI, all events will be counted in the numerator.

Confidence intervals [CI] will be computed using the exact method [[Clopper, 1934](#)].

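### The under-5 incidence has site start dates but no stop date, so after hospital surveillance closes, active-surveillance cases alone are divided by the whole census population

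*SAP*

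**What the plan says.** SAP 6.9.3.3 defines the secondary under-5 rate of each AESI, other AE leading to hospitalisation or death, and aetiology-confirmed meningitis. The numerator is cases "during the study period (in both AS and EHS grouped) and the denominator will be the person-years contribution of children in all communities" under 5 years, taken from the census. Results are given per year and overall. The same section starts the calculation at the field application of Protocol Amendment 4: Kombewa 9 March 2017, Kintampo 22 May 2017 (EHS) or 12 June 2017 (AS), Navrongo 25 September 2017. It gives no end date. Protocol 9.7.5.2.1 lets each child in the community contribute person-time until study end or the fifth birthday.

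The two surveillance arms end at different times.

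- **EHS.** Protocol 9.2.4 says "the enrolment in enhanced hospitalisation surveillance will end at start of study EPI-MAL-003". Protocol 9.1 says "study conclusion of EPI-MAL-002 for children enrolled in enhanced hospitalisation surveillance will be done at start of study EPI-MAL-003". Protocol 7.4 says EPI-MAL-003 "started in Q1 2019", and Protocol 9.9 adds that "the study start of EPI-MAL-003 might vary according to vaccination schedule and timing of vaccine implementation in each country".
- **AS.** Under Protocol 9.2.7.1.12, AS children not eligible for RTS,S or "declining vaccination will continue to be followed up to the study conclusion visit in EPI-MAL-002". SAP 7.2.13 caps last contact at 7 April 2022 (Kombewa), 27 April 2022 (Kintampo) and 19 July 2022 (Navrongo).

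The co-primary endpoints (Protocol 9.3.1, SAP 4.1) are framed as "In children living in the study area, prior to implementation of RTS,S/AS01_E". Protocol Table 7, which gives the precision of this same rate, assumes two years of follow-up ending before EPI-MAL-003 starts.

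**The concern.** A rate needs its events and its person-time to come from the same children over the same period. Here they match only while both arms are running. Once EHS closes, a hospitalised child outside AS can no longer become a case but still counts in the census denominator.

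The resulting bias is downward, in the overall rate and in every yearly rate after closure. By design, EHS closes when RTS,S becomes available, so the yearly series would show an artificial fall at exactly that point. The study exists to supply baseline rates for EPI-MAL-003, and a baseline that is too low could make post-implementation rates look raised.

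SAP 6.10.2.2 (meningitis groupings), 6.10.3 (cerebral malaria) and 6.10.5 (hospitalisation and death) reuse the method. Under-5 mortality may be diluted less if census death records also feed its numerator.

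**Working it through.** **Reproducing Table 7.** Person-years = 11,500 births × 5 age-years × 2 years = 115,000. With 25 events the rate is 25/115,000 = 21.7 per 100,000 PY. The exact Poisson limits, χ²(0.025; 50)/2 and χ²(0.975; 52)/2 divided by 115,000, give [14.1, 32.1]. This agrees with the protocol.

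**AS coverage.** The under-5 population implied by Table 7 is 115,000/2 = 57,500. AS in the analysed sites is about 20,000 (Protocol 9.7). Coverage c = 20,000/57,500 = 0.348. This is an upper bound, because AS children leave at age 5 or on RTS,S vaccination. Children born after AS recruitment ended enter the census but not AS. A second value, c = 0.20, is an assumption.

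**Time before and after closure.** The documents give no closure date by site, so three common dates are tried. The first two span Q1 2019 and the third is an assumption for a later start. Start dates are those of SAP 6.9.3.3 (Kintampo 22 May 2017) and end dates those of SAP 7.2.13. Years are listed in the order Kombewa, Kintampo, Navrongo.

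| Assumed closure | Years before | Years after | Share after |
|---|---|---|---|
| 1 Jan 2019 | 1.82, 1.61, 1.27 | 3.26, 3.32, 3.55 | 0.683 |
| 31 Mar 2019 | 2.06, 1.86, 1.51 | 3.02, 3.07, 3.30 | 0.634 |
| 30 Sep 2019 | 2.56, 2.36, 2.01 | 2.52, 2.57, 2.80 | 0.533 |

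**Dilution.** With sites equally weighted, observed/true = (pre + c × post)/(pre + post) = 1 − (1 − c) × share after. For 1 January 2019 and c = 0.348 this is 1 − 0.652 × 0.683 = 0.554.

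| Assumed closure | c = 0.348 | c = 0.20 | PY before closure |
|---|---|---|---|
| 1 Jan 2019 | 0.554 | 0.453 | 89,995 |
| 31 Mar 2019 | 0.587 | 0.493 | 104,006 |
| 30 Sep 2019 | 0.653 | 0.574 | 132,815 |

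The PY column is 57,500 × the mean number of years before closure. Person-time as written is 57,500 × the mean total years = 284,102 PY, against 115,000 in Table 7.

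**In rate terms.** With closure in Q1 2019, a true rate of 21.7 per 100,000 PY would read 21.7 × 0.554 to 21.7 × 0.587, about 12.0 to 12.7, at the higher coverage. It would read 21.7 × 0.453 to 21.7 × 0.493, about 9.8 to 10.7, at the lower. A full year after closure would read at most c, about 35% of the true rate.

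**Sensitivity.** Using 12 June 2017 for Kintampo gives 0.553, 0.585 and 0.651 at c = 0.348, a change of less than 0.3 percentage points. The protocol milestone for end of data collection is Q1 2022. Ending all sites on 31 March 2022 removes 7 + 27 + 110 days. For closure on 1 January 2019 the share after closure becomes 0.675 and the ratio 1 − 0.652 × 0.675 = 0.560 instead of 0.554.

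**The case against.** The best counter-argument is that a matched window was intended and is partly visible. The worked person-year example in SAP 6.9.3.3 is framed by the first and last subjects recruited. In this study the last recruit would be an EHS child, so the window would end at about EHS closure. Table 7 and the pre-implementation wording of the endpoints point the same way. The SAP also leaves the calculation method to a technical annex of the Mock TFL, which is not among the documents and may contain a stop date. On this view 284,000 PY is a worst case, because the SAP 7.2.13 dates cap an individual child's last contact and are not stated as the end of census person-time.

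Part of this stands. The intent was probably a matched window, and nothing here shows that the analysis was run the other way. But the example is an illustration with 2015-2017 dates and never mentions EHS closure. The one explicit rule on when this person-time ends, Protocol 9.7.5.2.1, says study end or age 5. If the example were read as stopping the denominator at last recruitment, the numerator would still run over the study period, and the rate would then be biased upward. Start dates are in the body of the SAP, and end dates belong beside them.

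It is also fair that AS children need not have the average under-5 event rate or the same case capture, so 35% bounds the rate only under that assumption.

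**Conclusion.** The concern holds. As written, the secondary under-5 rates mix a period with both arms running and a period with AS alone, over one whole-community denominator. The overall rate would be about 55%, 59% or 65% of the true rate at full AS retention, for closure on 1 January, 31 March or 30 September 2019. At an assumed 20% coverage it would be about 45%, 49% or 57%.

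These sizes assume one closure date for all three sites, equal site weights, a constant rate and under-5 population, and complete and equal case capture. They are conditional on the literal reading, and confidence in them is medium because the annex could not be seen. The direction of the bias under that reading does not depend on the exact closure date.

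Primary AS rates, and under-5 rates for years wholly before closure, are unaffected. The point should be fixed but does not threaten the main analysis.

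**What to change.** In SAP 6.9.3.3, and where 6.10.2.2, 6.10.3 and 6.10.5 reuse it, state an end date for each site equal to the actual EHS closure date there. Apply it to both events and census person-years, counted from the start date already given. Report AS events after that date only over AS person-time.

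The cost is a sentence and one date filter per site, mirroring the rule already used at the start of the window. AS events after closure drop out of this rate. Matched person-time would be about 90,000-104,000 PY for closure in Q1 2019 and about 133,000 PY for 30 September 2019. It equals Table 7's 115,000 at about 9 June 2019, so precision may fall somewhat short of the protocol's or exceed it, depending on the actual dates.

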
In children living in the study area, prior to implementation of RTS,S/AS01_E:

- Occurrence of probable meningitis (final classification).
- Occurrence of clinically suspected meningitis (final classification).
- Occurrence of meningitis cases identified at site level (first line laboratory).
- Occurrence of hospitalisation (including those attributed to an AESI, other AE, meningitis, or malaria) or death.
- Occurrence of febrile convulsions during the 7-day period (Days 0-6) and 1-month period (Days 0-29) following administration of routine EPI vaccines.
- Occurrence of two events used as surveillance quality indicators: abscess at injection site during the 7-day period (Days 0-6) following any routine vaccination and foot positional deformation.
- Occurrence of episodes of malaria using RDT and/or microscopy
 - Any malaria (including *P. falciparum* malaria).
 - Severe malaria (including *P. falciparum* malaria).
 - Cerebral malaria.
- Occurrence of anaemia at hospital entry among hospitalised children.
- Occurrence of hospitalisation
 - All causes and hospitalisations for any malaria (including *P. falciparum* malaria), severe malaria (including *P. falciparum* malaria) and cerebral malaria.

CONFIDENTIAL

115055 (EPI-MALARIA-002 VS AME)
Protocol Amendment 7 Final

- Occurrence of death
 - All causes and malaria attributed deaths (including *P. falciparum* malaria attributed death).
 - AE attributed deaths.

Data sources

HDSS (*or equivalent surveillance system*)

- Listings of all children living in the study area based on the demographic census;
- Total number of children < 5 years of age recorded at the beginning of the study, at least once a year during the study duration, and at the end of the study;
- Other demographic data (cause and date of deaths, migrations);
- Information related to vaccination.

Active surveillance (enrolment)

- Socio-demographic data;
- Active participation in any trial with an investigational product.

Active surveillance (home visits)

- Vaccination types and dates;
- Health history;
- Malaria control measures, health care seeking behaviour, drug use and exposure to environmental hazards;
- Verbal autopsy report.

Active surveillance (outpatient visits and hospitalisations at all health care facilities)

- Data on visits at primary health care facilities and hospitals since enrolment or last home visit.

Enhanced hospitalisation surveillance (hospitalisations)

- Socio-demographic data;

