Each AESI will be grouped as follows after case ascertainment for both confirmed and non-confirmed cases (see [Section 9.2.7.4.2](#)):

- Nerves and central nervous system: ADEM, encephalitis, Guillain-Barre Syndrome, HHE, generalised convulsive seizure.
- Hepato-, gastrointestinal and renal system: intussusception, hepatic failure or renal insufficiency.
- Skin and mucous membrane, bone and joints system: juvenile chronic arthritis, Stevens-Johnson syndrome/toxic epidermal necrolysis, Henoch-Schonlein purpura, Kawasaki disease.
- Systemic diseases and haematology: diabetes mellitus type I, thrombocytopenia, anaphylaxis.

The incidence following DTP/HepB/Hib vaccine or virtual vaccination using at-risk period described above will be estimated for the 6-12 weeks group and 5-17 months group.

Meningitis will not be grouped with other AESI and will be considered as a single endpoint (see case definition in [Section 9.2.5.3](#)).

CONFIDENTIAL115055 (EPI-MALARIA-002 VS AME)
Protocol Amendment 7 Final

Incidence rates of these composite endpoints will be calculated as described for individual AE leading to hospitalisation or death /AESI; in case of multiple cases in a subject, only the first event will be considered in this analysis.

All other AE leading to hospitalisation or death will be coded using Medical Dictionary for Regulatory Activities (MedDRA) Dictionary and presented by System Organ Class (SOC) and Preferred Term (PT).

Incidence following DTP/HepB/Hib vaccine or virtual vaccination will be computed for active surveillance only.

In addition, the incidence will be estimated for all children < 5 years. In such case, the person-time denominators for each rate will be reflective of the entire community population in the age group of interest. Each child will contribute person-time until the relevant age (at study end or at 5 years, whichever occurs first).

9.7.5.2.2. *Incidence rate of aetiology-confirmed meningitis*

Incidence rate (and 95% CI) of aetiology-confirmed meningitis (final classification based on second line laboratory results and after external panel of experts review) will be estimated with the same approach as for an AE.

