Because surveillance will be conducted in study areas covering mainly rural areas, children severely ill might die before being transported to hospital. In the event of death, the cause of death will be systematically documented through verbal autopsy using the INDEPTH Standard Verbal Autopsy Questionnaire* for children who died at home or medical judgment/medical records for children who died at a primary health care facility or hospital. However, ascertaining the cause of death remains a concern considering the limitation of the verbal autopsy methods in the field, this is why all-cause mortality is an important endpoint to consider in this study.

CONFIDENTIAL115055 (EPI-MALARIA-002 VS AME)
Protocol Amendment 7 Final

* If a site is not part of the INDEPTH network, or does not have an equivalent surveillance system in place, the INDEPTH procedures for verbal autopsy might be implemented to ensure consistency across study sites.

All efforts will be made to standardize data collection during EPI-MAL-002. However, due to the long duration of this study, changes in diagnostic procedures, implementation of malaria control measures such as seasonal malaria chemoprevention [WHO, 2012], and changes in treatment measures will have to be considered during the analyses of the safety and malaria data. Potential confounders will be collected at individual level during EPI-MAL-002, and at community level during EPI-MAL-005. Some subjects might also leave the study area during the study period but this is regularly documented through demographic census (scheduled at least once a year during the study periods).

To assess the vaccine effectiveness, the follow-up of an unvaccinated group during the EPI-MAL-003 study (post-implementation) is planned. However, there is an uncertainty about the recruitment of a sufficiently large unvaccinated group after the vaccine implementation of the RTS,S/AS01_E in those countries. The decision to collect information related to any malaria cases has been taken because the vaccine uptake may be very high and the number of unvaccinated children in EPI-MAL-003 may be too low to reliably estimate the direct vaccine effect. In this instance, the unvaccinated comparison group may have to be derived from EPI-MAL-002 only (estimations of the overall and total vaccine effects).

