#### **6.10.5. Cause of hospitalisation (including AESI, other AE, meningitis and malaria) and death**

Causes of hospitalisation (including AESI, other AE, classified by MedDRA SOC and PT level as well as meningitis and malaria) will be analysed grouped as follows:

- Hospitalisations (all causes)
- Hospitalisation for malaria (including *P. falciparum* malaria)
- Hospitalisation for *P. falciparum* malaria

In the same way, descriptive analysis of causes of death classified by MedDRA will be done overall and by gender grouped as follows:

- Deaths – all cause
- Malaria attributed deaths (including *P. falciparum* malaria)
- *P. falciparum* malaria attributed deaths
- Deaths attributed to an AESI or other AE (i.e. other than meningitis, AESI, malaria)

Descriptive analysis of the cause of hospitalisation (overall) and death (overall and by gender) will consist in computing the number of cases, person-year per 100,000 and IR (with 95% CI).

IR of all cause of hospitalisation and death will be computed following EPI vaccine or virtual vaccination (at risk period of 12 months) as described in section [6.9.3.2](#) and for children < 5 years as described in section [6.9.3.3](#). Of note, death IR per gender in children < 5 years will be computed after the first year of recruitment. Indeed, census per gender will be available after the application on field on the Protocol Amendment 4.

Note that malaria subtype will be defined using outpatient and hospitalisation visits. In case of death occurring at home malaria subtype may be unknown.

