### **7.2.3. Date of occurrence**

The dates of occurrence of events are defined as follows depending on the endpoint:

- Suspected or confirmed AESI and meningitis reported at hospital:
  - Onset date of event
- Suspected AESI and suspected meningitis reported during outpatient visit (see section [7.3](#) for worst case allocation sensitivity analysis):
  - Admission date at outpatient visit
- Other AE leading to hospitalisation or death:
  - Onset date of event if AE is the primary diagnosis
  - Admission date at hospital otherwise
- Suspected or confirmed malaria cases:
  - Onset date of event for hospitalised cases
  - Admission date at outpatient visit otherwise
- Death:
  - Date of death reported in study conclusion

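### The under-5 mortality rate counts deaths only in enrolled children but divides by the person-years of every child in the census, so it is biased low by an amount the documents do not give

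*SAP*

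**What the plan says.** SAP 6.9.3.3 defines the rate in children under 5. Cases are those "in both AS and EHS grouped) and the denominator will be the person-years contribution of children in all communities < 5 years of age", and "The denominator will be computed using the census data". Protocol 9.7.5.2.1 agrees on the denominator: "the person-time denominators for each rate will be reflective of the entire community population in the age group of interest".

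SAP 6.10.5 carries the rule over to death. It says that "IR of all cause of hospitalisation and death will be computed following EPI vaccine or virtual vaccination", and then sends the under-5 version to 6.9.3.3. In SAP Table 5 every death row, under a block covering both sexes together and each sex, has the symbol for AS plus EHS in the under-5 column.

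The event date for a death is the "Date of death reported in study conclusion" (SAP 7.2.3). SAP 7.2.12 takes the cause from the same form.

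Protocol 9.2.2 controls who can have such a form. AS needs consent and an age below 18 months at enrolment. EHS needs consent and a hospital stay.

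The protocol abstract lists the HDSS as a source of "Other demographic data (cause and date of deaths, migrations". As a source of deaths for a rate, however, the HDSS register is named only in protocol Table 8 and SAP Table 4, both confined to AS children.

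**The concern.** Numerator and denominator describe different populations. A child who is in neither AS nor EHS and who dies at home stays in the census person-time but has no form from which a death could be read. This can happen to an infant who dies before first DTP without being admitted, to a child too old for AS who is never admitted, and to a child whose parents declined. The protocol expects deaths outside hospital: its limitations section (9.9) warns that "children severely ill might die before being transported to hospital".

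The secondary objective is the mortality rate in children of the study area, overall and by sex. Protocol 7.2 explains that sex-specific mortality is classed as missing information in the risk management plan. An under-5 rate that loses an unknown share of deaths is a poor baseline for that question. If home death or access to hospital differs between girls and boys, the loss also distorts the comparison between them.

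**Working it through.** **1. Reproduce the plan's denominator.** Protocol Table 7 uses a birth cohort of 11,500 and 2 years of follow-up. Person-years = 11,500 × 5 ages × 2 = 115,000, as printed. The exact Poisson interval for 25 events is 21.7 per 100,000 PY [14.1, 32.1], also as printed. The denominator is therefore the whole under-5 population, 11,500 × 5 = 57,500 children.

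**2. Share in AS.** Protocol 9.7 gives about 20,000 AS children in the analysed sites. f = 20,000 / 57,500 = 0.348. The other 0.652 can supply a death only after EHS enrolment.

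**3. Formula.** Let c be the share of deaths outside AS that occur in EHS-enrolled children, whether in hospital or later at home. With equal mortality inside and outside AS, and all AS deaths captured:

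observed / true = f + (1 − f) × c = 0.348 + 0.652c

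**4. Scale.** Protocol 7.2 cites under-5 mortality of 3% to 5%. Taking 3%, spread evenly over five years (an assumption): 0.03 / 5 = 600 per 100,000 PY, or 690 deaths in 115,000 PY. Deaths counted = 690 × (0.348 + 0.652c) = 240 + 450c.

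| c | observed/true | deaths counted | rate per 100,000 PY [95% CI] |
|---|---|---|---|
| 1 | 1.00 | 690 | 600.0 [556.1, 646.5] |
| 0.9 | 0.93 | 645 | 560.9 [518.4, 605.9] |
| 0.75 | 0.84 | 578 | 502.6 [462.5, 545.3] |
| 0.5 | 0.67 | 465 | 404.3 [368.4, 442.8] |
| 0.25 | 0.51 | 353 | 307.0 [275.8, 340.7] |

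At c = 0.75 and below, the interval excludes the assumed true value of 600. With this many deaths the error is bias, and the confidence interval would not reveal it.

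**5. Sex ratio.** If c were 0.75 in one sex and 0.5 in the other, with the same f and no true difference, the observed ratio would be 0.674 / 0.837 = 0.81, an apparent deficit of about 19%. This only illustrates the mechanism; the documents give no value of c by sex.

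**6. Other features that push the same way.** The analysis is on the ATP cohort (SAP 6.9.1, 6.10.1), so deaths of eliminated participants leave the numerator while their time stays in the census. EHS ends when EPI-MAL-003 starts (protocol 9.2.4, 9.2.7.2.15), whereas protocol 9.7.5.2.1 runs census person-time to study end or age 5. I have not quantified either.

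**The case against.** The strongest reply is that the mortality objective does not depend on this rate. SAP 6.11 with Tables 3 and 4 divides deaths in AS children by AS person-years, with home visits and the HDSS register among the sources, and Table 5 lists these analyses overall and by sex. That stands. A reader might infer that the study has no sound mortality estimate; the documents do not support that.

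A reader might also infer that a co-primary result is compromised. The main co-primary population is AS, and AS plus EHS is explicitly secondary (protocol 9.7.5.1, SAP 6.9.1). SAP 6.9.2.2 classifies other AEs for hospitalised cases, which EHS is designed to find. AESI and meningitis also depend on hospital diagnosis. These under-5 rates are much less affected.

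Nor is every home death outside AS lost. A child enrolled in EHS at an earlier admission is followed to study conclusion, and SAP 6.9.3.1 reads home deaths from that form. A calculation that treats all non-AS home deaths as missed would overstate the bias, which is why the formula above uses c.

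Finally, SAP 6.9.3.3 defers the method of computing incidence to a technical annex of the mock tables, which is not available here. It could add HDSS deaths. Nothing in the SAP says that it does, and SAP 7.2.3 and 7.2.12 point to the study conclusion form.

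None of these points removes the mismatch in the under-5 death rate or reverses its direction.

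**Conclusion.** As written, the under-5 death rates, overall and by sex, are biased low, because never-enrolled children who die at home are in the denominator but cannot enter the numerator. The sex ratio may be biased as well if capture differs by sex.

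The direction follows from the text. The size does not: c is not in the documents. The 35% is a ratio of planned head-counts, not of analysed person-time, and equal mortality inside and outside AS is an assumption. Under those assumptions the rate would be about 16% too low at c = 0.75, 33% at c = 0.5 and 49% at c = 0.25. No single figure should be quoted as the bias.

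The fault is confined to a secondary output, but it should be corrected or disclosed before that output is presented as mortality in the study area.

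**What to change.** In SAP 6.9.3.3 and 6.10.5, take the all-cause under-5 death numerator, overall and by sex, from the HDSS death register for all census children under 5. State one area and one start and end date for both the deaths and the census person-years.

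Report cause-specific under-5 death rates, such as malaria-attributed death, only where the HDSS verbal-autopsy cause is usable, with the caveat that cause is less certain for children who were never enrolled.

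If HDSS deaths are not used, drop the death rates that put AS plus EHS over the census, or label them minimum estimates. Report AS deaths over AS person-years as the mortality rate.

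For all-cause death the cost is SAP wording and one further extract from a system that already supplies the denominator and records deaths with dates and causes. Cause-specific rates cost more, because deaths of non-enrolled children would need cause coding without study case-report data. Relabelling costs only wording.

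If the technical annex already adds HDSS deaths, the SAP should say so.
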